#### 3.2 OVERALL SCHEDULE OF TIMES AND EVENTS

Study Procedures	Baseline 	Treatment Phase			
Study Week		Week 4 	Week 12 	Follow-up Visits (every 12 weeks through study termination) 	Week 108 / Study Termination Visit
Informed Consent 	X				
Subject Eligibility 	X				
SGRQ 	X			X 	X
Physical Examination 	X				X
Vital Signs 	X	X	X	X	X
Clinical Laboratory Assessments 	X	X	X	X	X
N-terminal proBNP 	X			X 	X
Blood sample for biomarker evaluation (optional) 	X			X 	X 
Urine Pregnancy Test 	X	X	X	X	X
Peak 6MWT 	X	X	X	X	X
Pulse Oximetry 	X	X	X	X	X
Documentation of Supplemental Oxygen Requirement	X	X	X	X	X
PFTs 	X		X	X 	X
Dosing instructions / Dosing / Accountability	X	X	X	X	X
Telephone/Email Contact 		X	X	X	
Adverse Events 	X	X	X	X	X
Concomitant Medications	X	X	X	X	X
Hospitalizations 	X	X	X	X	X
Exacerbations of Underlying Lung Disease 	X	X	X	X	X

- NT-ProBNP: N-terminal brain natriuretic peptide; PFTs: pulmonary function tests; PH: pulmonary hypertension; SGRQ: St. George Respiratory Questionnaire; 6MWT: six-minute walk test
-  Baseline assessments (6MWT, pulse oximetry, PFTs, SGRQ, clinical laboratory assessments, NT-ProBNP, urine pregnancy test, optional biomarker sample [as applicable], vitals, and physical examination) for this study are those collected at the Study Termination Visit (Week 16) from study RIN-PH-201 and prior to initiation of open-label study drug. Informed consent and subject eligibility criteria are exclusive to this protocol.
-  The visit window for the Week 4 visit is ± 5 days; the visit window for all other visits is ± 14 days. Visits are scheduled based off of the day of first dose of study drug for the RIN-PH-202 study (i.e., four weeks after the first dose of study drug in this open-label study).

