#### 3.3.1.2 St. George's Respiratory Questionnaire

The SGRQ will be conducted at Baseline as part of the Study Termination (Week 16) assessments from protocol RIN-PH-201. The SGRQ will also be conducted at Week 48 and at Week 108/Study Termination. The SGRQ should be completed as the first assessment during these visits before the subject completes any of the other scheduled visit assessments. A copy of the SGRQ can be found in Appendix 15.3.

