#### 3.3.1.3 N-terminal pro-brain natriuretic peptide (NT-proBNP)

Plasma NT-proBNP concentration is a useful biomarker associated with changes in right heart morphology and function (Fijalkowska 2006). NT-proBNP sample collection will occur at Baseline as part of the Study Termination (Week 16) assessments from protocol RIN-PH-201. NT-proBNP will also be collected at Week 48 and at Week 108/Study Termination. Blood for NT-proBNP assessment must be drawn prior to conducting the 6MWT.

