#### 3.3.2.4 Pulmonary Function Tests (PFTs)

Pulmonary Function Tests (PFTs) will be assessed at Baseline as part of the Study Termination (Week 16) assessments from protocol RIN-PH-201 and at Week 12, Week 48, and at Week 108/Study Termination. If the PFT is done both prior to and after a

bronchodilator, only the pre-bronchodilator values will be recorded. Pulmonary function tests should be conducted after recovery from the 6MWT.

The following parameters will be recorded (absolute values and % predicted): FEV1, FVC, TLC, and DLCO (uncorrected for hemoglobin and lung volume).

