#### 7.3 WEEK 108 / STUDY TERMINATION VISIT

The Week 108 visit will be the Study Termination Visit. In addition, if a subject discontinues the study prior to Week 108, they will complete a Study Termination Visit. If possible, each subject should remain on study drug until they have completed the Study Termination Visit. The following assessments will occur at the Study Termination Visit:

- SGRQ (questionnaire must be administered prior to any results, procedures, or blood draws)
- Physical examination
- Vital signs (following at least five minutes of rest; collected prior to 6MWT or after recovery from the 6MWT)
- Urine pregnancy test, for women of childbearing potential
- Blood draws for clinical laboratory parameters
- NT-proBNP (must be drawn prior to 6MWT)
- Collection of blood sample for evaluation of biomarkers (optional; only in those subjects who discontinue prior to Week 48)

\*Assessments conducted during the Week 48 visits ONLY.

- Peak 6MWT (must be conducted between 10 to 60 minutes after the most recent dose of study drug and following at least 10 minutes of rest [sitting])
- Pulse oximetry (to be performed immediately prior to, throughout the conduct of, and immediately following the 6MWT)
- Documentation of supplemental oxygenation requirement (L/min)
- PFTs (to be performed after recovery from the 6MWT)
- Hospitalizations due to a cardiopulmonary indication
- Exacerbations of underlying lung disease
- Adverse events
- Concomitant medications
- Study drug accountability

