8.4 ASSESSMENT WINDOWS

For efficacy and safety assessments, Baseline is defined as the last measurement prior to the first dose of inhaled treprostinil in the RIN-PH-202 study.

The assessments will be mapped into the analysis visit windows based on Table 8-1.

Table 8-1 Assessment Windows for Scheduled Visits

Visit	Target Study Day	Study Day Interval
Baseline	1	Study Day \leq 1
Week 4	29	$1 < \text{Study Day} \leq 57$
Week 12	85	$57 < \text{Study Day} \leq 127$
All other visits	169, 253, etc	Target Study Day ± 42

Note: Study Day = (Assessment Date) - (First inhaled treprostinil Dosing Date) +1

8.4.1 *Multiple Evaluations Within the Same Analysis Window*

After all the observations have been assigned according to Table 8-1, if there are multiple valid observations for an assessment within an assigned analysis visit window, only one of these observations will be used for summary statistics. The observation to be used will be determined using the following hierarchy (in decreasing order):

- The observation closest to the target study day
- The later observation if 2 observations are equally close to the target study day.

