12 APPENDICES**12.1 LIST OF TABLES**

Table Number	Table Title
14.1.1	Summary of Subject Accountability
14.1.2	Summary of Inhaled Treprostinil Exposure
14.1.3	Summary of Inhaled Treprostinil Exposure in RIN-PH-201 and RIN-PH-202 Studies
14.1.4.1	Summary of Entry Criteria Violation
14.1.4.2	Summary of Protocol Deviations
14.1.5	Summary of Demographics
14.1.6	Summary of Baseline Characteristics
14.1.7	Summary of PH-ILD History
14.1.8.1	Summary of Concomitant Medications Ongoing from RIN-PH-201
14.1.8.2	Summary of Concomitant Medications Added during the RIN-PH-202 Study
14.1.9	Summary of Inhaled Treprostinil Dosing and Exposure
14.1.10	Summary of Inhaled Treprostinil Treatment Compliance
14.2.1.1	Summary of 6MWD (meter) by Visit
14.2.1.2	Summary of NT-proBNP (pg/mL) by Visit
14.2.1.3.1	Summary of SGRQ Total Score by Visit
14.2.1.3.2	Summary of SGRQ Symptoms Score by Visit
14.2.1.3.3	Summary of SGRQ Activity Score by Visit
14.2.1.3.4	Summary of SGRQ Impacts Score by Visit
14.2.1.4	Summary of Distance Saturation Product (m%) by Visit
14.3.1.1	Overall Summary of Adverse Events
14.3.1.2	Summary of Adverse Events by System Organ Class and Preferred Term
14.3.1.3	Summary of Adverse Events by Preferred Term
14.3.1.4	Summary of Deaths
14.3.1.5	Summary of Serious Adverse Events by System Organ Class and Preferred Term
14.3.1.6	Summary of Non-Serious Adverse Events by System Organ Class and Preferred Term
14.3.1.7	Summary of Adverse Events Probably or Possibly Related to Study Drug by System Organ Class and Preferred Term

Table Number	Table Title
14.3.1.8	Summary of Adverse Events Leading to Permanent Discontinuation of Study Drug by Preferred Term
14.3.1.9	Summary of Adverse Events by System Organ Class, Preferred Term, and Severity
14.3.1.10	Summary of Adverse Events by Study Drug Dose at AE Onset
14.3.2.1	Listing of Deaths
14.3.2.2	Listing of Serious Adverse Events
14.3.3.1	Summary of SpO ₂ (%) Measured by Pulse Oximetry by Visit
14.3.3.2	Summary of SpO ₂ Category by Visit
14.3.3.3	Summary of Heart Rate (beats/min) Measured by Pulse Oximetry by Visit
14.3.3.4	Summary of Supplemental Oxygen Use by Visit
14.3.3.5	Summary of Supplemental Oxygen Use (L/min) by Visit
14.3.3.6	Summary of Pulmonary Function Tests by Visit
14.3.3.7	Summary of Subjects with $\geq 20\%$ Decrease in FEV ₁ from Baseline
14.3.4.1	Summary of Laboratory Data – Clinical Chemistry
14.3.4.2	Summary of Clinical Chemistry Shifts from Baseline by Visit
14.3.4.3	Summary of Laboratory Data – Hematology

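### The SAP has no rule for early-termination values: under Table 8-1 most SGRQ, NT-proBNP and PFT ones would fall in weeks where those assessments are not scheduled, and some termination walks leave the by-visit summaries

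*SAP*

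**What the plan says.** Protocol 7.3 says that "if a subject discontinues the study prior to Week 108, they will complete a Study Termination Visit". That visit includes SGRQ, NT-proBNP, the peak 6MWT with oximetry, and PFTs.

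Otherwise these assessments follow different schedules:
- SGRQ (Protocol 3.3.1.2): "The SGRQ will also be conducted at Week 48 and at Week 108/Study Termination".
- NT-proBNP (Protocol 3.3.1.3): "NT-proBNP will also be collected at Week 48 and at Week 108/Study Termination".
- PFTs (Protocol 3.3.2.4): after Baseline, "at Week 12, Week 48, and at Week 108/Study Termination".
- 6MWT, and so DSP: every scheduled visit.

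The SAP uses one date-based grid for all of them. Section 8.4 states: "The assessments will be mapped into the analysis visit windows based on Table 8-1". If several values share a window, 8.4.1 says that "only one of these observations will be used for summary statistics": the one closest to target, or the later one in a tie.

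Sections 10.1–10.4 and 11.6 summarize by visit. Section 12.1 follows suit, for example with "Summary of SGRQ Total Score by Visit", and lists no early-termination table. Section 8.2 gives withdrawal reasons and rules out imputation, but does not say how termination values are displayed. Section 8 keeps all data in listings.

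**The concern.** A termination visit can fall on any study day. A grid built for scheduled visits therefore handles its values in ways that nobody chose.

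For SGRQ, NT-proBNP and PFTs, a value is filed under a week at which the rest of the cohort was never due to be assessed. A termination SGRQ on Day 250, for instance, becomes a Week 36 SGRQ. Because summaries are made at each analysis visit, the literal result is a Week 24, 36 or 60 row made up almost only of subjects who were leaving. A reader could take that row for a cohort time point.

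For 6MWD and DSP every window is a scheduled row, so the issue differs. A termination walk can lose to an earlier walk in the same window and drop out of the summary.

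For many subjects who leave before Week 48, the termination visit supplies the only SGRQ and NT-proBNP after Baseline. Endings caused by commercial availability would be mixed with clinical ones in the same rows. At stake is whether the descriptive tables that serve the secondary objective are correctly labelled and complete.

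**Working it through.** **Reproducing Table 8-1.** Target day = 7 × week + 1, giving 29, 85, 169, 253, 337, 421, 505, 589, 673 and 757 for Weeks 4, 12, 24, …, 108. Limits are midpoints: (29 + 85)/2 = 57; (85 + 169)/2 = 127; 84/2 = 42. These match the SAP. The windows are Days 2–57, 58–127, 127–211, 211–295, 295–379, 379–463, 463–547, 547–631, 631–715 and 715–799.

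**Overlap.** With closed ±42 limits, Days 127, 211, 295, 379, 463, 547, 631 and 715 each lie in two windows. No visit held within the protocol's own visit windows lands on them, but a termination visit can.

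**Share in unscheduled windows.** Assumption: termination days spread evenly over Days 2–756 (755 days).
- SGRQ and NT-proBNP: the Week 48 window has 85 days (295–379) and the Week 108 window 42 days before target (715–756), together 127. Unscheduled: (755 − 127)/755 = 628/755 = 83.2%.
- PFTs: the Week 12 window adds 70 days (58–127). Unscheduled: (628 − 70)/755 = 558/755 = 73.9%.
- Stopping at Day 742, before the protocol's Week 108 visit window opens, removes 14 scheduled days: 628/741 = 84.8% and 558/741 = 75.3%.
- Other timings tested were constant hazard with 30–90% stopped by Week 108, and even timing within Days 2–180, 2–365, 180–560 and 366–742. With the even case, they give 78–100% for SGRQ and NT-proBNP and 61–89% for PFTs.

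**Termination walks left out by 8.4.1.** Assumptions: even timing over Days 2–742, all visits attended, shared days assigned to the earlier window. The base is walks made after at least one attended visit.
- Visits exactly on target: every termination day after target in the same window is displaced. Week 4 gives 28 days (30–57), and Weeks 12 to 96 give 8 × 42 = 336. Total 364. Base: Days 30–742 = 713. 364/713 = 51.1%. With shared days assigned to the later window, (364 − 8)/713 = 49.9%.
- Visits spread evenly over the protocol's allowance (±5 days at Week 4; otherwise "the visit window for all other visits is ± 14 days"): a walk t days after target is displaced if the attended walk is closer. Per later window this gives 28 days (t = 15–42) plus the sum of (2t − 1)/29 for t = 1–14, which is 196/29 = 6.76; together 34.76. Week 4 gives 23 + 25/11 = 25.27. Total 8 × 34.76 + 25.27 = 303.3. The base is again 713 (708 full days plus 55/11 = 5). 303.3/713 = 42.5%; a simulation gave 42.4%.
- In that simulation 49% of these walks fall in the next window and are kept there, and 9% replace the attended walk because they are closer or tied.
- If subjects terminate at the scheduled visit itself, none is displaced.

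**The case against.** Rule 8.4.1 is not an error. A by-visit table needs one value per subject per window. Closest-to-target is prespecified, does not depend on the outcome, and keeps each row near its labelled week. The subject stays in the row, and the other walk stays in the listing. All of this stands, and the rule should remain for the by-visit rows.

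A reader might infer that any walk made after an attended visit is lost. The documents do not support that: the walk must share a window with an attended walk that is closer to target. Most of the others are summarized under the next visit's label.

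A reader might also infer that off-schedule SGRQ, NT-proBNP and PFT values end up only in listings. The SAP summarizes at each analysis visit and uses all available data, so the natural reading is that these rows are printed. The defect is then mainly one of labelling.

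Other outputs give partial cover: reasons for discontinuation (SAP 9.1), adverse events leading to discontinuation, and Kaplan-Meier analyses of death, hospitalization and exacerbation. Table 14.3.3.7, on FEV1 decreases of at least 20%, states no visit basis and may use termination PFTs. None of the others summarizes the termination values of these endpoints.

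Finally, a separate termination row pools very different study days. It could also mix walks on and off drug, because Protocol 7.3 asks subjects to stay on drug until that visit only where possible. Both points stand and shape the fix.

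**Conclusion.** The gap is real and should be closed. The SAP does not say how Study Termination Visit values are summarized. Under even timing, about 83% of early-termination SGRQ and NT-proBNP values and 74% of PFT values land in windows with no scheduled assessment. They are a majority under every timing pattern tested. About 42–51% of termination walks made after an attended visit leave the 6MWD and DSP by-visit summaries under even timing, and 0% do so if termination coincides with the scheduled visit.

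These shares rest on assumed timing. The documents give neither a dropout rate nor its distribution, so numbers of subjects cannot be derived from them. It would be tempting to conclude that the long-term results are biased in a favourable direction. The documents do not support that: the study is uncontrolled, no formal hypothesis testing is planned, and neither direction nor size can be stated. The consequence is limited to mislabelled or incomplete descriptive summaries. The eight shared boundary days are a minor addition.

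**What to change.** 1. In SAP 8.4, 10.2, 10.3 and 11.6, state that SGRQ, NT-proBNP and PFT termination values do not enter week rows where that assessment is not scheduled.
2. In SAP 10.1–10.4, 11.6 and 12.1, add one labelled early-termination display for 6MWD, DSP, SGRQ, NT-proBNP and PFTs, by parent-study group and overall. Show n, value, change from Baseline, study day, reason (administrative versus other) and whether the subject was still on study drug; for walks, also show time since last dose. Carry no value forward. Keep 8.4.1 for the by-visit rows, but do not let it remove values from this display.
3. After Week 12, define windows as Target − 41 to Target + 42 (Week 24 = Days 128–211, Week 36 = Days 212–295, and so on).

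Counts of attrition at each visit and a supportive repeated-measures model are optional.

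The cost is SAP wording and modest programming, with no new data. Reasons for discontinuation and last dose dates are already listed under SAP 9.1, and hours from last dose to walk under SAP 10.1. The downside is that the display pools different study days, so study day must be shown beside the values. It cannot include subjects who die or are lost without a termination visit.

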#### 3.3.2.2 Vital Signs

Vital signs will be assessed at Baseline as part of the Study Termination (Week 16) assessments from protocol RIN-PH-201 and at each subsequent study visit and at the Study Termination Visit. Vital signs measured will include blood pressure (systolic and diastolic), heart rate (HR), respiratory rate (RR), temperature, and weight. Vital signs must be assessed following at least five minutes of rest (sitting) to ensure accurate measurement. No other measurements or procedures should be performed during this five-minute period. When applicable, vital signs should be collected prior to the 6MWT. If vital signs cannot be obtained prior to the 6MWT, they should be obtained after recovery from the 6MWT. Vital signs should also be assessed in the case of abnormal clinical signs and symptoms.

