3 STUDY DESIGN

This is a multicenter, open-label study. Subject visits will occur at Baseline, Weeks 4, 12, and every 12 weeks thereafter until Week 108. The study will continue until each subject has completed Week 108 or until inhaled treprostinil becomes commercially available for patients with pre-capillary pulmonary hypertension associated with interstitial lung disease (PH-ILD) including CPFE (whichever is sooner).

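### SAP Table 8-1 places eight study days in two analysis visits each, and Section 8.4.1 does not say which visit owns a value on such a day

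*SAP*

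**What the plan says.** SAP Section 8.4 counts days by date: "Study Day = (Assessment Date) - (First inhaled treprostinil Dosing Date) +1". Table 8-1 then maps each assessment to a window. The Week 4 and Week 12 rows exclude the lower limit and include the upper one, which gives Days 2 to 57 and Days 58 to 127. All later visits share one row, with targets 169, 253 and so on, and the window "Target Study Day ± 42". SAP Section 3 gives the schedule behind that row: "Subject visits will occur at Baseline, Weeks 4, 12, and every 12 weeks thereafter until Week 108".

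Section 8.4.1 governs the summaries once the mapping is done: "if there are multiple valid observations for an assessment within an assigned analysis visit window, only one of these observations will be used". The value nearest the target is preferred, then "The later observation if 2 observations are equally close to the target study day".

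The Baseline row takes every value with Study Day ≤ 1. The sentence above the table is narrower: "Baseline is defined as the last measurement prior to the first dose of inhaled treprostinil in the RIN-PH-202 study". SAP Section 11.8 repeats the pre-dose definition for vital signs.

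**The concern.** Analysis windows should place each assessment in exactly one visit. Here the later windows include both end days, and their half-width of 42 days is exactly half the spacing between targets, so each window shares its end day with the next. Section 8.4.1 settles competition between values inside a window; it does not settle competition between windows for one value. A programmer who follows the table literally enters the same measurement in two visit summaries. One who notices the overlap must invent a rule that the SAP does not record.

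The assessments exposed are the off-schedule ones. Protocol Section 7.3 requires a Study Termination Visit from any subject who discontinues before Week 108, so such assessments are expected and can fall on any study day.

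**Working it through.** **Inputs.** Windows, targets and the study-day formula: SAP Table 8-1. Visit weeks: SAP Section 3. Visit tolerance of ±5 days at Week 4 and ±14 days otherwise: Protocol Section 3.2, footnote 2. Collection schedule for each measure: Protocol Sections 3.3.1 and 3.3.2. Expected enrolment of 266: SAP Section 6. Assumption: the table's open-ended list of targets continues in 84-day steps to Week 108, as the schedule implies.

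**Targets reproduced.** Target = 7 × week + 1 gives 29, 85, 169 and 253 for Weeks 4, 12, 24 and 36, as in the table. Continuing gives 337, 421, 505, 589, 673 and 757 for Weeks 48 to 108.

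**Literal windows**

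| Visit | Days | Last day shared with next visit |
|---|---|---|
| Week 12 | 58–127 | 127 |
| Week 24 | 127–211 | 211 |
| Week 36 | 211–295 | 295 |
| Week 48 | 295–379 | 379 |
| Week 60 | 379–463 | 463 |
| Week 72 | 463–547 | 547 |
| Week 84 | 547–631 | 631 |
| Week 96 | 631–715 | 715 |
| Week 108 | 715–799 | none |

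Eight days fall in two windows. Each is 42 days from both targets (for example 127 − 85 = 42 and 169 − 127 = 42), so nearness to target cannot decide. That is 8 of the 798 days from Day 2 to Day 799 (1.0%), or 8 of the 755 days from Day 2 to Day 756, before the Week 108 target (1.06%). Since 42 exceeds 14, no visit held within tolerance reaches a shared day.

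**When one value is used twice.** Applying Section 8.4.1 to example patterns:

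- 6MWD on Days 29, 85 and 127: Day 85 is nearer the Week 12 target, so Day 127 is used once, at Week 24.
- 6MWD on Days 29 and 127, Week 12 missed: Day 127 is used at Weeks 12 and 24.
- SGRQ or NT-proBNP at termination on Day 211: used at Weeks 24 and 36.
- PFT on Day 85 and at termination on Day 211: Day 211 is used at Weeks 24 and 36.
- SGRQ on Day 337 and at termination on Day 379: Day 337 holds Week 48, so Day 379 is used once, at Week 60.

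Double use therefore needs a shared day and no closer value in either window. Measures taken at every visit meet the second condition only after a missed visit. SGRQ and NT-proBNP (Week 48 and Week 108/termination) and PFTs (also Week 12) usually meet it.

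**Expected number of subjects.** Assume that 30%, 50% or 70% of 266 terminate early, on days spread evenly over Days 2 to 756. The expected number terminating on a shared day is 266 × rate × 8/755:

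- 30%: 79.8 × 0.0106 = 0.8
- 50%: 133 × 0.0106 = 1.4
- 70%: 186.2 × 0.0106 = 2.0

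These count terminations on a shared day, so for termination visits they are upper figures for double use.

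**After the edit.** With Target − 42 < Study Day ≤ Target + 42, every day up to Day 799 falls in exactly one window, with no overlap and no gap.

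**The case against.** The strongest reply is that this changes nothing of substance. Protocol Section 10.3 plans no formal hypothesis testing, SAP Section 8.2 imputes nothing, on-time visits are unaffected, and for 6MWD, laboratory tests, vital signs and oximetry an on-time earlier visit normally holds its own window. One repeated value in a visit mean would alter no conclusion. All of that stands, and it sets the size of the point. It does not supply the missing allocation rule.

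A reader might infer something stronger from the Baseline row. Table 8-1 maps by date alone, so a vital sign taken after the first dose on Day 1 carries the Baseline label, and Section 8.4.1 read alone would prefer it as the later of two Day 1 values. Protocol Section 3.3.2.2 offers a route: "Vital signs should also be assessed in the case of abnormal clinical signs and symptoms". From there one might conclude that first-dose reactions fall into Baseline and bias every later change. The documents do not support this. The sentence above the table requires a pre-dose value, and SAP Sections 9.3.2, 10.1 to 10.4, 11.5.1 and 11.8 repeat that requirement. Adverse events are selected by onset on or after the first dose (SAP Section 11.1), not by window. Protocol Sections 3.2 and 7.1 schedule no post-dose measurement on Day 1. What remains is a mismatch between the table row and the governing definition.

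**Conclusion.** The overlap is real and exact: eight study days each belong to two analysis visits, and the SAP has no rule for a value on one of them. Followed literally, the table can summarise one assessment at two visits, most plausibly a termination SGRQ, NT-proBNP or PFT, or any measure after a missed visit.

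The effect is minor: about 1% of study days, and at most about 1 to 2 subjects under the assumed 30% to 70% early termination with an even spread of days. Neither assumption comes from the documents. Unscheduled and very late assessments are not in that count. The Day 1 row is a wording inconsistency only; change from Baseline is protected by the pre-dose definition.

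**What to change.** In Table 8-1, replace the row for later visits with Target − 42 < Study Day ≤ Target + 42. Week 24 becomes Days 128 to 211, Week 36 Days 212 to 295, and so on to Week 108 at Days 716 to 799. This continues the convention of the Week 4 and Week 12 rows, where the day midway between two targets goes to the earlier visit.

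In the Baseline row, add that the value must also precede the first RIN-PH-202 dose, so that the row agrees with Sections 8.4 and 11.8. No extra Day 1 summary row is needed, since no post-dose Day 1 measurement is scheduled.

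The cost is two edits to one SAP table. No new data or outputs are needed: the SAP already lists first-dose date and time (Section 9.1) and vital-sign date and time (Section 11.8).

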#### 15.2 GUIDELINES AND DEFINITIONS FOR RECORDING ADVERSE EVENTS

The Investigator or a designated member of his/her staff will probe each subject for any AEs that may have occurred. The Investigator should always ask the same question when conducting the verbal probe in order to ensure uniformity between subjects. The Investigator should ask:

"How are you doing (feeling)?"

Based on the subject's response to this question, the Investigator should ask additional questions relevant to the specific complaint such as:

"How severe is/was the symptom?"

"How often did the symptom occur?"

"How long did the symptom last?"

It is the Investigator's responsibility to review the results of all diagnostic and laboratory tests as they become available and ascertain if there is a clinically significant change from Baseline. If the results are determined to be a clinically significant change from Baseline, this should be reported as an AE. The Investigator may repeat the diagnostic procedure or laboratory test or request additional tests to verify the results of the original tests. When possible, a diagnosis associated with the abnormality should be used as the reported AE.

Using provided definitions, the Investigator will then:

(1) rate the intensity and seriousness of the AE, (2) estimate the causality of the AE to study drug, and (3) note actions taken to counteract the AE.

Definitions of Intensity, Seriousness, Causality, Action Taken, and Outcome

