11.7 CLINICAL LABORATORY TESTS

The following clinical chemistry parameters will be evaluated by the central laboratory:

Parameter	Units
Sodium	mmol/L
Potassium	mmol/L
Bicarbonate	mmol/L
Chloride	mmol/L
Total bilirubin	umol/dL
Alkaline phosphatase	U/L
Alanine aminotransferase	U/L
Aspartate aminotransferase	U/L
Urea nitrogen	mmol/dL
Creatinine	umol/L
Calcium	mmol/L
Albumin	g/L

The following hematology parameters will be evaluated by the central laboratory:

Parameter	Units
Hemoglobin	g/dL
Hematocrit	%
Red blood cell count	10 ⁶ /uL
Red blood cell morphology	
White blood cell count	10 ³ /uL
Platelet count	10 ³ /uL

Values that are “high” or “low” with respect to the reference range provided by the central laboratory will be flagged with an “H” or an “L,” respectively. All parameters will be listed for all subjects and assessments, along with their respective “high/low” flags.

Values of these parameters at each visit, and their corresponding changes from Baseline, will be descriptively summarized by parent study treatment group and overall.

For each parameter, the frequency and percentage of subjects within each parent study treatment group and overall who had “low,” “normal,” or “high” Baseline values, then subsequently had “low,” “normal,” or “high” follow-up values at each visit, will be presented in a shift summary.

Pregnancy test results for female subjects will be summarized by parent study treatment group and overall and listed by subject number, analysis visit, and pregnancy status.

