11.8 VITAL SIGNS

Vital sign results will be mapped to analysis visit based on assessment date. The vital sign data will be listed by subject and parent study treatment group for each analysis visit by assessment date/time (day), weight, heart rate, blood pressure, respiration rate, and temperature. The original measures and their changes from Baseline (defined as the last measurement prior to the first inhaled treprostinil dosing in the RIN-PH-202 study) will be summarized for all analysis visits by the parent study treatment group and overall.

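### Laboratory and vital-sign tables keep one value per window, the one nearest the target day (SAP 8.4.1), and no worst-value table shows the recorded values this leaves out

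*SAP*

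**What the plan says.** SAP 8.4 opens by naming both kinds of data when it defines Baseline: "For efficacy and safety assessments, Baseline is defined as the last measurement prior to the first dose". The next sentence is general: "The assessments will be mapped into the analysis visit windows based on Table 8-1". Where a window holds several valid values, 8.4.1 states that "only one of these observations will be used for summary statistics". First in its hierarchy is "The observation closest to the target study day", then the later value if two are equally close. Nothing exempts safety data, prefers a scheduled value or prefers an abnormal one.

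The safety sections follow the same by-visit layout:

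- SAP 11.7 summarizes laboratory values and changes at each visit, and its shifts are by visit too: "follow-up values at each visit, will be presented in a shift summary".
- SAP 11.8 maps vital signs to analysis visits by date. Values and changes "will be summarized for all analysis visits by the parent study treatment group and overall". No vital-sign shift table is planned.
- The table list in SAP 12.1 (14.3.4.1 to 14.3.4.5) contains no worst-value or any-time laboratory or vital-sign table. It does include a count of subjects with a fall of at least 20% in FEV1 (14.3.3.7).

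The protocol foresees values between visits. Section 3.3.2.2 says: "Vital signs should also be assessed in the case of abnormal clinical signs and symptoms". Appendix 15.2 says: "The Investigator may repeat the diagnostic procedure or laboratory test or request additional tests to verify the results of the original tests". Section 3.3.2.3 provides for further tests, where appropriate, to document that an abnormality has resolved. Section 7.3 gives subjects who leave early a Study Termination Visit with laboratory tests and vital signs.

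**The concern.** Choosing the value nearest the target day is a sound way to build a mean over time. It is a poor way to show how often abnormal values occurred, because selection depends on the calendar and not on the value. Vital signs taken because a subject has symptoms are, by their purpose, more likely than routine ones to be abnormal, and they will usually lie further from the target day than the routine visit does.

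Protocol 2.2 lists laboratory parameters and vital signs as safety endpoints separate from AEs, and section 3.3.2 counts changes in them among the main safety assessments. If a platelet count falls and recovers between two visits, both shift rows can show a normal value. The listing holds the low count, but a listing gives no incidence by group.

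**Working it through.** The documents give no figure for this point, so there is none to reproduce. The question is how often an unscheduled value replaces the scheduled one under 8.4.1.

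**Inputs from the documents**

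- Analysis windows (SAP Table 8-1): Week 4, days 2 to 57, target 29; Week 12, days 58 to 127, target 85; later visits, target ± 42 days. Adjoining windows share a boundary day, so for Week 24 (target 169) I count days 128 to 211.
- Window lengths: 56, 70 and 84 days.
- Visit windows (Protocol 3.2, footnote 2): ± 5 days at Week 4, ± 14 days otherwise.

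**Assumptions not in the documents**

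- One scheduled value, equally likely on any day of the visit window.
- One unscheduled value, equally likely on any other day of the analysis window.

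**Formula.** Let the scheduled visit be d days from target. There are 2d − 1 days strictly closer to target. If the visit was early, the mirror day d days after target also wins, because the later value takes a tie. So the unscheduled value wins on 2d days when the visit is early, 2d − 1 days when it is late, and never when d = 0. Divide by the window length minus 1.

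To average over visit days, sum (2d) + (2d − 1) = 4d − 1 over d and divide by the number of visit days:

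- Week 4: d = 1 to 5 gives 60 − 5 = 55; 55/11 = 5 winning days; 5/55 = 9.1%.
- Week 12: d = 1 to 14 gives 420 − 14 = 406; 406/29 = 14 winning days; 14/69 = 20.3%.
- Week 24 and later: 14 winning days; 14/83 = 16.9%.

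| Window | Kept, visit on target | Kept, visit at edge (late / early) | Kept, average | Left out, average |
|---|---|---|---|---|
| Week 4 | 0% | 9/55 = 16.4% / 10/55 = 18.2% | 9.1% | 90.9% |
| Week 12 | 0% | 27/69 = 39.1% / 28/69 = 40.6% | 20.3% | 79.7% |
| Week 24+ | 0% | 27/83 = 32.5% / 28/83 = 33.7% | 16.9% | 83.1% |

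**Illustration.** Suppose the Week 24 visit falls on day 172, 3 days late. Only an unscheduled value on days 167 to 171 would replace it: 5 of the other 83 days, or 6%. A value on day 200 would be left out.

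**Early-termination values.** Table 8-1 has no termination row, so these values compete under the same rule. Assume that termination is uniform over a ± 42-day window, that the scheduled visit is at offset d (uniform within ± 14 days), and that it was attended only if it came before termination. The termination value loses when it falls more than |d| days after target, with probability (42 − |d|)/84. That is 42/84 = 50% at d = 0 and 28/84 = 33% at |d| = 14. With a mean |d| of 7 it averages 35/84 = 42%.

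**The case against.** The strongest reply is that the AE tables already catch what matters. Protocol 3.3.2.3 requires a laboratory abnormality judged clinically significant to be reported as an AE, and Appendix 15.2 says the same of a clinically significant change in any diagnostic or laboratory result. The symptom that prompts an extra blood pressure reading will often be an AE itself. SAP 11.1 summarizes AEs without regard to visit windows. This stands. A reader might infer that off-target readings never reach any safety summary, and the documents do not support that.

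The AE route is still not a full substitute. It depends on the investigator's judgement of significance, which a shift table does not need. Protocol 9.2 prefers a diagnosis to its component signs, and 9.1.1 excludes signs of the studied disease unless they are more severe than expected. The vital-signs section has no explicit counterpart to the laboratory AE rule.

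Other objections also limit the point:

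- Repeat laboratory tests are optional or done where appropriate. They often confirm or follow up an abnormal scheduled value, and then the value left out may be the normal one.
- An unscheduled value is used when it is nearest the target or alone in its window.
- The documents do not say whether symptom-triggered vital signs or local repeat tests are entered in the database, and SAP 11.7 speaks of the central laboratory.
- The study is descriptive. A data monitoring committee reviews safety, every laboratory value is listed with high and low flags, and SAP 1 allows additional analyses.

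These points lower the stakes. They do not supply an incidence of abnormal values that is independent of the visit windows.

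**Conclusion.** The point holds as a gap in the planned laboratory and vital-sign tables. Where a scheduled value shares the window, about 80% to 91% of unscheduled values are left out of those tables on average, as are roughly 33% to 50% of early-termination values in windows of ± 42 days. Both ranges rest on the assumed uniform timing, and the first applies only to unscheduled values that are recorded.

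They are shares of values not selected. It would be tempting to read them as the share of harms or of affected subjects missed. The documents do not support that, because they give no frequency of unscheduled readings and no information on how many are abnormal. Nor would a subject who is hypotensive between visits appear as normal in a shift row, since vital signs have no shift table; the reading would simply be missing from the by-visit summary.

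What is missing from every summary is mainly transient abnormality that was not reported as an AE. That justifies a cheap improvement to the SAP. It does not mean the safety analysis as a whole fails.

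**What to change.** Keep SAP 8.4.1 for by-visit summaries and say that it applies to those only. Then:

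- **SAP 11.7:** for parameters with a reference range, add a shift from Baseline to the worst post-Baseline low value and, separately, to the worst post-Baseline high value.
- **SAP 11.8:** add a summary of each subject's vital-sign extremes, namely lowest systolic blood pressure and highest heart rate.
- **Both:** use all recorded scheduled, unscheduled and termination values from the first open-label dose to study termination, by parent-study group and overall, with exposure shown in the header or a footnote. State that 8.4.1 does not apply.
- **Data source:** state whether unscheduled vital signs and local repeat laboratory tests are in the database, and so whether they count.
- **SAP 12.1:** add the new tables.

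The cost is some SAP wording and about three tables (chemistry, hematology, vital signs), with no new data collection for values already recorded. The drawback is that extremes rise with length of follow-up and number of tests, so they need to be read against the exposure shown.
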